4.6 STUDY IMAGES

At all sites, the images in the study will be obtained using the 2D Quantificare digital photo system and software for image collection, storage, and analysis. To ensure consistent, reproducible study photos from baseline photographs to the follow-up photographs, Quantificare photography guidelines and procedures must be followed, see **Attachment H**. Site personnel will be trained on these guidelines at the Investigator Meeting. The following photographs should be obtained at each study visit, for each imaging system used:

- Screening/Baseline 2D photographs, capturing 5 views: Frontal View; Right and Left Lateral (90°); Right and Left Oblique (45°);
- Immediate Post-treatment Standard 2D photographs, capturing 3 views: Frontal View; Right and Left Lateral (90°).
- 90 Day Follow-Up Standard 2D photographs, capturing 5 views: Frontal View; Right and Left Lateral (90°); Right and Left Oblique (45°);

- Day 180 Follow-Up Standard 2D photographs, capturing 5 views: Frontal View; Right and Left Lateral (90°); Right and Left Oblique (45°);
- Day 365 Follow-Up Standard 2D photographs, capturing 5 views: Frontal View; Right and Left Lateral (90°); Right and Left Oblique (45°);

Subjects' Screening/Baseline images are considered the pre-treatment comparator images. Screening/Baseline images may be taken within 14 days prior to study treatment. ***Subject photos must be reviewed prior to study treatment to ensure proper subject selection and photographic quality.***

At up to 3 sites (in up to 135 subjects), additional images will be obtained using a 3D Quantificare system, see **Attachment I** (these images will be used only for marketing purposes). To ensure consistent, reproducible study photos from baseline to follow-up, Quantificare's photography guidelines and procedures must be followed, see **Attachment H**. Site personnel will be trained on these guidelines on an individual basis by Quantificare prior to study enrollment.

In order to carefully control the positioning of the subject for reproducible photos at each time point the Quantificare positioning device will be utilized at all sites for the all photographs, both 2D and 3D. The system is composed of a pair of thin/light weight glasses equipped with lasers that subjects will wear during the photo session. The lasers will be projected on the wall facing the subject. By positioning their head the laser will be aligned with a target on the wall, standardizing the head position at each time point. Additional details and procedures regarding the Quantificare system are available in **Attachments H**.

5. TREATMENT OF SUBJECTS AND FOLLOW-UP

This study involves one treatment to be conducted at the treatment visit after obtaining informed consent, screening for inclusion/exclusion, complying with standardized photography requirements, completing a pregnancy test, if applicable, and completing randomization.

5.1 STUDY TREATMENT

5.1.1 TRANSDUCERS

Two types of the Standard transducers with Energy Level 2 (EL2) will be used during this trial:

1. 4 MHz with a 4.5mm focal depth
2. 7 MHz with a 3.0mm focal depth

Two types of the Simulines transducers with EL2 will also be used:

1. 4MHz with a 4.5mm focal depth
2. 4MHz with a 3.0mm focal depth.

The region to be treated and the transducer used must be appropriately selected on the Ulthera® system and thus recorded on the Treatment Parameter System Record. The Ulthera system will default to EL2 with the study sites instructed not to adjust the energy level.

5.1.2 PRE-TREATMENT MEDICATIONS

For this protocol, pre-treatment medications will be restricted to Ibuprofen (800mg) taken by all subjects at least 60 minutes but not more than two hours prior to study treatment.

[figure not shown]
5.1.3 SUBJECT PREPARATION FOR TREATMENT

The investigator, sub-investigator, or qualified study staff member will first mark the skin areas to which an Ulthera® treatment is to be performed (**Figure 5.1.3-1**). Treatment schematic is for illustrative purposes only. Treatment records for all regions will be maintained in accordance with this protocol.

[REDACTED]

[REDACTED]

[REDACTED]

5.1.4 TREATMENT

All study treatments will be performed by the investigator, sub-investigator, or qualified study staff member (i.e., study treatment clinician as designated by the principal investigator.) The study clinician performing efficacy assessments should remain blinded to the assigned treatment group, and therefore may not perform study treatments.

Ultrasound gel will be applied to the transducer, which will then be placed on the targeted skin surface, and ultrasound image will be obtained. Each area of the proposed treatment will be imaged first with the ultrasound device to ensure coupling between the transducer and skin. During the treatment procedure, the study treatment clinician will place multiple Ultherapy[®] treatment lines close to each other in the selected area, with each treatment line requiring about 3 seconds. When using the Simulines transducer the distance the transducer should be advanced between delivery of treatment lines should be doubled as 2 lines of treatment are laid down simultaneously. It is also recommended that at least 2 to 3 passes are used to deliver all lines in each section to allow for tissue cooling between passes of energy delivery. Treatment lines can be a maximum length of 25mm and will produce a series of thermal coagulative points.

Treatment lines to the area highlighted in (Figure 5.1.3-1) above will be administered as specified by Treatment Group. Energy joules delivered for study treatments will be 0.9J joules [EL2] for the Standard 4-4.5mm transducer and 0.30J [EL2] for the Standard 7-3.0mm transducer. [REDACTED]

All study treatments will begin with the 4.5mm depth. The entire 4.5mm depth treatment will be completed prior to continuing to the 3.0mm depth treatment. Treatment will be delivered in a lined pattern. The subject will be monitored during the treatment.

The time each treatment begins and ends will be captured and recorded on the source documents.

5.1.5 ACUTE RESPONSES

For all exposures, acute responses (e.g., erythema or edema) will be observed by the study treatment clinician and photographically recorded within 30-60 minutes after exposure. If any Serious Adverse Events are noted, an AE Form should be completed.

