3. STUDY PROCEDURES

3.1 SCHEDULE OF ASSESSMENTS AT EACH STUDY VISIT

Table 3.1-1 provides an overview of the subject screening procedure, baseline evaluation, treatment plan, and follow-up requirements.

TABLE 3.1-1: SCHEDULE OF ASSESSMENTS

Evaluation / Procedure	Screening Visit	Baseline Visit ⁺	Treatment Visit ⁺	Telephone Contact Day 3 ± 1D Day 7 ± 2D	Day 90±14 Follow-up	Day 180±21 Follow-up	Day 365±30 Follow-up
Informed Consent	√						
Eligibility Assessment (Inclusion/Exclusion ¹)		√ ⁴					
Demographics and Medical History		√					
Pregnancy Screening [^]		√					√
Skin Examination ²		√	√				
Treatment of Face and Neck			√				
Collection of Treatment Time from System Treatment Log			√				
Subject Assessment of Pain ³			√				
2D images; 3D Images (at applicable site(s))	√	√ ⁴	√ ⁵		√	√ ⁶	√ ⁶
Masked Qualitative Assessments					√	√	√
Jawline Scale		√			√		
Patient Satisfaction Questionnaire					√		
Clinician Global Aesthetic Improvement Scale - CGAIS					√	√	√
Subject Global Aesthetic Improvement Scale - SGAIS					√	√	√
Clinician Blinding Questionnaire							√
Subject Blinding Questionnaire							√
Adverse Event Assessment		*	*	*	*	*	*

+Baseline and Treatment Visits may be separate visits or combined into one visit.

[^] Pregnancy:

- a. If a subject becomes pregnant after the Baseline visit and after study treatment, the subject should continue to be followed.
- b. If a subject becomes pregnant after the Baseline visit but before study treatment, the subject should be exited from the study.

*Complete AE Form when necessary.

NOTES:

1. Baseline Form
2. Baseline Clinical Observations (Pre-Treatment) or Clinical Safety and Adverse Events (Post-Treatment and at Follow-up Intervals).
3. Subject Pain Assessment Scale using a validated Numeric Rating Scale. Pain scores should be obtained following each region treated and for each transducer used. Record the average pain score for the entire region treated.
4. Baseline assessment and pre-treatment photos should be obtained within 14 days of study treatment. Screening photos may be used as Baseline photos
5. Post-treatment images taken 30-60 minutes following Ultherapy® treatment for documentation of immediate post-treatment AEs.
6. Images taken on this visit, but not a primary endpoint for efficacy.

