6.5 SAFETY ANALYSES

The safety analysis will be performed using subjects in the intent-to-treat population. The safety outcome will be incidence of all treatment-emergent adverse events, where “treatment-emergent” is defined as beginning or worsening after treatment initiation. Incidence of device-related adverse events will also be summarized separately.

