7.1 DEFINITIONS

An adverse event is defined as any new medical problem, or exacerbation of an existing problem, experienced by a subject while enrolled in the study, whether or not it is considered device-related by the investigator. During data analysis the Sponsor will evaluate all reported events and may re-categorize some events as expected treatment effects based on the following definition:

- **Expected Treatment Effect:** Any typical treatment side-effect of Ultherapy® of mild to moderate severity and lasting up to a typical maximum duration (see Figure 7.1.1 and Table 8.1.1).

All reported adverse events should be re-assessed by follow-up contact with the subject every 7 days until resolved.

FIGURE 7.1.1: EVENT REPORTING

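### Section 5.1.5 ties the AE form at the 30-60 minute acute check to serious events only, which conflicts with the AE definition, the safety outcome and the visit schedule and risks uneven recording of brief reactions

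*Combined protocol and SAP*

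**What the plan says.** Section 5.1.5 (Acute Responses) covers reactions such as erythema or edema just after treatment. They "will be observed by the study treatment clinician and photographically recorded within 30-60 minutes after exposure". The section then gives its one instruction about forms: "If any Serious Adverse Events are noted, an AE Form should be completed".

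The protocol treats adverse events more broadly elsewhere:

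- Section 7.1: "An adverse event is defined as any new medical problem, or exacerbation of an existing problem, experienced by a subject while enrolled in the study". Device relatedness is not required, and neither is seriousness.
- Section 7.1, on what happens afterwards: "During data analysis the Sponsor will evaluate all reported events and may re-categorize some events as expected treatment effects".
- Section 6.5: "The safety outcome will be incidence of all treatment-emergent adverse events", where treatment-emergent is "defined as beginning or worsening after treatment initiation".
- Synopsis, Treatment Outline, item 6: adverse events are assessed immediately after treatment, with no limit to serious ones.
- Table 3.1-1: the adverse event row is marked in the Treatment Visit column. Its footnote calls for a form where one is needed but does not say when that is. Note 5 gives the purpose of the photographs: "Post-treatment images taken 30-60 minutes following Ultherapy® treatment for documentation of immediate post-treatment AEs".

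**The concern.** Section 5.1.5 is the text specific to the acute check, and a treating clinician would naturally turn to it for what to write down. Read literally, it calls for a form only when the event is serious. A site that follows it may photograph a non-serious reaction and go no further. A site that follows Section 7.1 would complete a form for the same reaction. Each could believe it had complied.

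This matters because the objective in Section 2.1 covers safety as well as efficacy, and Section 6.5 measures safety by adverse event incidence. With a single energy treatment, the first hours are where many reactions would be expected, and the comparison is between one line per pulse and two. Section 2.2 also makes wider enrollment depend on FDA approval of a safety report after the first 15 subjects, so early events may be used before the trial is complete.

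**Working it through.** The point rests on no sample size, rate or margin, and the plan gives no figure to reproduce. The check sets the sections side by side.

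**1. Is the acute check inside the safety window?** Yes. Section 6.5 counts events "defined as beginning or worsening after treatment initiation", and the 30-60 minute check falls after initiation.

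**2. Does a non-serious acute reaction qualify as an adverse event?** By the definition, yes: "An adverse event is defined as any new medical problem, or exacerbation of an existing problem". Section 7.4 makes seriousness a separate classification applied to an event that is already an adverse event.

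**3. Who sorts out expected effects, and when?** Under Section 7.1 the sponsor does so, during data analysis, from events already reported. Table 8.1.1 lists erythema, edema, bruising, welting and others as expected effects. The order is report first, classify second. An SAE-only trigger at the site lets filtering happen before that step.

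**4. Do other provisions tell the site what to do?**

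| Provision | Covers non-serious acute events? | Says when a form is required? |
|---|---|---|
| Section 5.1.5 | Observed and photographed | Only for serious events |
| Synopsis, item 6 | Yes, assessed | No |
| Schedule, AE row at Treatment Visit | Yes, assessed | Left to need, undefined |
| Schedule, note 2 (skin examination) | Yes, names a clinical safety and adverse events record after treatment | No |
| Schedule, note 5 (images) | Yes, documented by photograph | No |
| Day 3±1 and Day 7±2 calls | Yes, adverse events captured | No |
| Section 5.2, later visits | Yes, adverse events queried | No |

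The intent to collect all adverse events is clear, but among these treatment-visit and follow-up provisions only 5.1.5 attaches a condition to the form.

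**5. Which events are exposed?** The first contact after the visit is at Day 3±1, so between 2 and 4 days, or 48 to 96 hours (2 × 24 to 4 × 24). Maximum durations in Table 8.1.1, set against that window:

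- Erythema and edema, up to 72 hours: a reaction lasting the full 72 hours is present at a 48-hour call and over by a 96-hour call. Shorter ones may be gone in either case.
- Acute pain, up to 2 hours: over before any call.
- Welting up to 1 week, burn and nodules up to 4 weeks, muscle weakness up to 6 weeks: at or near these durations they would still be present at the first call.

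Exposure is concentrated in brief reactions, where capture at the call would depend on recall.

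**6. Can the under-count be sized?** No. The earlier studies summarized in Section 1.6 give the only related counts for the face and neck: three device-related events, all welting, in the 70-subject study (3/70 = 4.3% of subjects at most), and no adverse events in the studies of 15 and 35 subjects. The protocol does not say whether those counts left out expected effects, and the 70-subject study used 290 lines against a minimum of 672 pulses, one line each, in Group A here. No document gives the share of reactions that clear before the first call or are forgotten by then.

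**The case against.** The strongest reply is that 5.1.5 only says what to do about serious events. It does not use the word only, and it does not excuse a site from Section 7.1. The synopsis, the schedule and its note 2 all provide for adverse events at the Treatment Visit, and the calls are not limited to events still present. Figure 7.1.1, on event reporting, is not available in the text reviewed and may give a clearer route. The reactions most likely to be missed are also ones the sponsor may later re-categorize as expected effects, so they could drop out of the adverse event tables even with every form completed.

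Most of this stands, and it rules out two stronger readings. A reader might infer that non-serious acute events go uncounted. The documents do not support that, because 5.1.5 forbids nothing and several other routes exist. A reader might also infer that the safety comparison is biased between arms, since the treating clinician handles the transducer and so knows the assignment. The rule is the same in both arms and no passage points to different reporting. The clinician's knowledge of assignment is a separate matter that rewording 5.1.5 would not change.

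The reply does not remove the conflict. No provision listed above tells a site which rule governs the form at the acute check. Later re-categorization is the sponsor's decision on reported events, which differs from events never being reported.

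**Conclusion.** Wrong as written. The trigger in Section 5.1.5 is inconsistent with Sections 7.1 and 6.5, the synopsis and the schedule. The supportable consequence is a risk of under-recording and of site-to-site inconsistency in non-serious acute events, greatest for short-lived erythema and edema. Its size cannot be computed from the documents, and any percentage would rest on assumed rates. The conclusion assumes that at least some sites would take 5.1.5 as the working rule and that Figure 7.1.1 does not already settle the matter. The primary efficacy analysis is not affected.

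**What to change.** In Section 5.1.5, replace the reference to serious adverse events with one to adverse events as defined in Section 7.1, whether or not serious, applied identically in both arms. Leave classification of expected effects to the sponsor step already in Section 7.1. State that pain during energy delivery continues to be recorded on the Numeric Rating Scale under Section 5.2. Requiring a form for every effect in Table 8.1.1 would go too far, because that table includes momentary pain while energy is delivered, and potentially most subjects would then have an adverse event.

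The change is one sentence plus brief site training. It alters no treatment, endpoint or sample size. It does bring more forms, more follow-up contacts (Section 7.1 has each reported event re-assessed every 7 days until it resolves) and a higher reported count of mild events.

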5.1.6 POST-TREATMENT SUNSCREEN

Subjects will apply study-supplied sunscreen daily until Study Exit to help limit sun exposure.

5.2 SAFETY VARIABLES

Prior to treatment, the subject's medical history will be reviewed, a urine pregnancy test will be performed (if applicable), and a physical examination will be conducted. During Ultherapy[®] treatment, the subject's pain levels will be monitored using a validated Numeric Rating Scale (Attachment D). Average pain scores should be obtained following each region treated and for each transducer used during treatment. The average pain score for the entire region treated by each transducer will be recorded. A script will be used for collecting pain scores.

At each subsequent visit, the subject will be queried about adverse events and changes in concomitant medications, and the treatment area will be visually examined. A second pregnancy screening test will be performed at the 365-day follow-up visit.

5.3 QUANTITATIVE MEASURES

Submandibular/Submentum quantitative measurements calculated as detailed in **Attachment A**, comparing subjects treated using Simulines versus Standard transducers, will be obtained based on 2D study images obtained at follow-up visits post-treatment compared to baseline.

Comparison of improvement data for overall lifting and tightening of skin as determined by a masked, qualitative assessment of photographs obtained at follow-up visits post-treatment compared to baseline as detailed in **Attachment F**.

Secondary effectiveness will be assessed at baseline and 90 days using the validated, Merz Jawline Grading Scale (MJGS) (**Attachment G**) by independent, masked evaluators using photographs obtained at baseline and the 90-day follow-up visit. The evaluators will be trained and qualified on the MJGS by the sponsor and will remain masked throughout the study. The MJGS is an ordinal scale and ratings will be made based on a “snap-shot” at a single point in time and therefore will not be based on a comparison to a pre-treatment photograph.

The Global Aesthetic Improvement Scale (GAIS) (**Attachments B and C**) will be obtained at all post-treatment time points. The GAIS is a 5-point scale that rates global aesthetic improvement from the pre-treatment appearance. The ratings are worse, no change, improved, much improved, and very much improved. It was validated by [name], et al. for this use. In this study, both live observation and photo review are utilized by the clinician (CGAIS) and subject (SGAIS) in order to assign a score. The CGAIS must be performed by the primary investigator, or a qualified study staff member delegated by the PI. Both the CGAIS and SGAIS should be completed in two steps:

- Based on a live assessment of the subject while referring to the subject’s pre-treatment photographs (subjects should be given a hand mirror for this assessment); and
- Based on a comparison of the subject’s pre-treatment photographs to the current post-treatment photographs.

A validated Numeric Rating Scale (0-10) (**Attachment D**) will be used to record subjects’ pain scores during study treatment. Scores will be obtained for each region treated and for each transducer used.

A Patient Satisfaction Questionnaire (PSQ) (**Attachment E**) will be completed at the 90-day follow-up visit. The subject should complete this assessment while referring to baseline photos and using a hand mirror as well as comparing baseline and follow-up photographs.

The time to complete the study treatment for each group will be captured as treatment start time (time treatment started on the Ulthera System) and stop time (time treatment is ended on the Ulthera System) automatically recorded on the system treatment logs. The treatment logs are the source documents that are referred to when recording treatment times on the case report forms.

Volumetric changes from baseline compared to 90, 180, and 365 days post-treatment will be assessed using Quantificare 3D imaging as a secondary outcome measure at up to 3 sites. Please see **Attachment J**.

5.3.1 PRIMARY ENDPOINT

Efficacy will be assessed based on quantitative measurements of neck and submental lift at 90 days post-treatment compared to baseline. Subject response is defined as ≥ 20 mm² reduction in 2D submental area from baseline.

(Note: this is the same methodology and success criteria which supported the FDA clearance of the submental/neck lift indication for this device). Simulines transducers will be considered non-inferior to Standard transducers using a non-inferiority margin of 15% between the two study arms. The study was powered based on the expected response rate of 73% as seen in the pivotal trial supporting the neck/submental lift indication FDA clearance K121700. The observed response rate of the prior pivotal trial (73%) was higher than the minimum response rate required (65%) for success of the supporting trial.

5.3.2 SECONDARY ENDPOINTS

The secondary endpoints of this clinical trial include:

1. Subject response as measured by quantitative improvement measurements of submandibular and submental lift at 180 and 365 days post-treatment compared to baseline.
2. Comparison of improvement in overall lifting and tightening of skin as determined by a masked, qualitative assessment of photographs at 90, 180 and 365 days post-treatment compared to baseline.
3. Assessment of mean change from baseline to 90 days post treatment on the validated, Merz Jawline Grading Scale (MJGS) by independent masked evaluators.
4. Quantificare 3D imaging of up to 135 study subjects to assess volumetric changes from baseline compared to 90, 180, and 365 days post-treatment.
5. Patient satisfaction and patient reported improvement at 90 days post-treatment.
6. Comparison of average treatment times using Simulines transducers compared to average treatment times using Standard transducers.
7. Comparison of average pain scores using a validated Numeric Rating Scale to assess subjects' treatment-related comfort level with Simulines transducers versus Standard transducers.
8. Subject Global Aesthetic Improvement Scale (SGAIS) results assessing overall aesthetic improvement at 90, 180 and 365 days post-treatment.
9. Clinician Global Aesthetic Improvement Scale (CGAIS) results assessing overall aesthetic improvement at 90, 180, and 365 days post-treatment.

